## 16. SAFETY ENDPOINTS

Summaries of safety data will be based on the safety analysis set. There will be no statistical comparisons between the treatment groups for safety data, unless otherwise specified with the relevant section.

### 16.1 ADVERSE EVENTS (AEs)

AE is any untoward medical occurrence in a patient or clinical investigation patient, temporally associated with the use of a medicinal product, whether or not considered related to the medicinal product.

Adverse events will be collected from the start of the study drug until the Follow-Up contact. Serious adverse events will be recorded from the time of consent up to and including any follow up contact.

Adverse Events will be coded using MEDDRA 21.1 or higher version.

Treatment emergent Adverse Events (TEAEs) are defined as AEs which commence on or after the time of start of IP administration. Adverse events without an onset date or time or AEs with an onset date of the date of IP administration but without an onset time will be defined as treatment emergent, except if an incomplete date (e.g., month and year) clearly indicates that the event started before administration of IP or if the AE stop date indicates that the event stopped before administration of IP.

See Appendix 2 of the SAP for handling of partial dates for AEs.

Listings will include all AEs (TEAEs and Non-TEAEs).

Document: \\ieedc-vnasc01\Biosdata\Reistone\SHR0302\CZA55021\Biostatistics

Author: [REDACTED]

Version Number:

Final v1.2

Version Date:

23Mar2021

Template No: CS\_TP\_BS016 Revision 5  
Effective Date: 01Apr2018

Reference: CS\_WI\_BS005

Summaries of the incidence of AEs within each of the categories described below, will be provided.

### **16.1.1 All TEAEs**

An overall summary of TEAEs in treatment phase will be provided. The number and percentage of patients experiencing AEs and the number of TEAEs will be tabulated.

Incidence of TEAEs will be presented by System Organ Class (SOC) and Preferred Term (PT) and summarized in treatment phase for each SHR0302 dose level , placebo and overall.

All TEAEs during the whole study period will also be summarized for the following groups similarly.

- 8 mg QD total: 8mg QD during the whole study period+ Placebo->8mg QD group after treatment phase
- 4 mg BD total: 4 mg BD during the whole study period + Placebo->4mg BD group after treatment phase
- 4 mg QD total: 4 mg QD during the whole study period + Placebo->4mg QD group after treatment phase
- Placebo only: Placebo group during treatment phase

Incidence of TEAEs will also be broken down further as shown in the following sections.

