1.3 Study Design

This is an 8+8 weeks, randomized, double-blind, multi-center, placebo controlled, parallel group study to include adult patients with moderate to severe active Ulcerative Colitis. The study consists of an 8-week blinded treatment phase, followed by 8-week of blinded active arms extension phase. The primary endpoint is assessed at the end of treatment phase at week 8.

Eligible subjects will be randomized to either one of the 3 doses of active drugs or placebo in 1:1:1:1 ratio for 4mg QD, 4mg BD, 8mg QD and placebo group respectively for treatment phase. The total number of subjects to be randomized is 152. There will be a total of 9 outpatient clinic visits. Subjects randomized into placebo in treatment phase will also have a pre-assigned randomized treatment sequence for extension phase, which are 3 active groups (placebo -> 4mg QD, placebo -> 4mg BD, and placebo -> 8mg QD) in a 1:1:1 ratio. Subjects randomized to the active arms for treatment phase will remain in the same dose group in the extension phase.

At Visit 1 (screening), subject will be screened and if the subject meets the inclusion/exclusion criteria, the subject can be consented and enrolled into the study with a subject identifier number.

At Visit 2 (Day 0), subject will be randomized into the study if there is no further change to subject's criteria.

After randomization, the subject will be followed-up at week 1, week 4, and week 8, corresponding to Visit 3, Visit 4, and Visit 5 at treatment phase respectively. At Visit 5 (week 8) the primary endpoint assessment will be conducted. Following this treatment phase, subjects have the option to enroll into a further 8 weeks of active arms extension phase.

All subjects that have completed the initial 8 weeks (non-responders or responders) have the option to enter a blinded active arm 8-week extension phase according to the group they were randomized to for extension phase. All subjects have the option not enrolling into the extension phase after first 8 weeks of treatment. All subjects in the extension phase are followed-up for further 2 weeks until week 18 (last visit). Subjects who have completed the first 8-week of treatment phase, but decided not entering into extension phase are required to attend the 2-week follow-up visit. Early withdrawn subjects during the first treatment phase cannot enter the extension phase.

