The total duration of the study participation, including extension and follow-up, will be approximately 18 weeks.

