## 13. STUDY MEDICATION EXPOSURE

Exposure to study medication will be presented for SS by treatment group.

The date of first study medication administration will be taken from eCRF “Noncompliance with study treatment ” form if available (Site will check medical chart and make the first dose record on this eCRF form). In case of not available, the first dose date from the diary data will be used. The date of last study medication will be taken from the eCRF “End of Treatment”

Document: \\ieedc-vnasc01\Biosdata\Reistone\SHR0302\CZA55021\Biostatistics  
Author: [REDACTED]

Version Number:  
Version Date:

Final v1.2  
23Mar2021

Template No: CS\_TP\_BS016 Revision 5  
Effective Date: 01Apr2018

Reference: CS\_WI\_BS005

form. In the case of missing data on the eCRF, the last dose date from diary data will be used

The study medication intake for each day will be taken from the diary “Time of Dosing” and “# Tablets Taken” items. The following information will be summarized for each treatment group in treatment phase, extension phase and overall:

- Duration of Exposure (days)
- Planned number of study drug tablets
- Actual number of study drug tablets
- Number of Dosing Days
- Cumulative Dose (mg)
- Average Daily Dose (mg/day)

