### **16.1.2 TEAEs of Serious Infection**

A serious infection during the study is defined as any infection (viral, bacterial, and fungal) requiring hospitalization or parenteral antimicrobials. The patient must be discontinued from the study. Serious infection will be identified as those records with a response of "Yes" to the item "Is this a serious infection defined in protocol?" on the "Adverse Events" form of the eCRF. Serious Infection in treatment phase will be summarized by SOC and PT for each SHR0302 dose level , placebo and overall. The number of patients with at least one serious infection will be presented and 95% CI will be calculated using the Clopper-Pearson method. TEAEs of serious infection will also be summarized similarly for 8 mg QD total, 4 mg BD total, 4 mg QD total, Placebo only and overall during the whole study period.

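### The whole-study AE tables set crude percentages from up to 18 weeks of observation on each dose beside 8 weeks of placebo, so they cannot be read against placebo

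*SAP*

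**What the plan says.** SAP 16.1.1 plans two sets of TEAE tables. The first covers the treatment phase, by dose, placebo and overall: "The number and percentage of patients experiencing AEs and the number of TEAEs will be tabulated". The second extends this: "All TEAEs during the whole study period will also be summarized for the following groups similarly". The first group listed is "8 mg QD total: 8mg QD during the whole study period+ Placebo->8mg QD group after treatment phase", the 4 mg BD and 4 mg QD totals follow the same pattern, and the last is "Placebo only: Placebo group during treatment phase".

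The same columns return for relationship (16.1.1.1), severity (16.1.1.2), discontinuation (16.1.3), SAEs (16.1.4), fatal TEAEs (16.1.5), deaths (16.2) and maximum QTcF (16.4.1). For serious infection, 16.1.2 says "TEAEs of serious infection will also be summarized similarly for 8 mg QD total, 4 mg BD total, 4 mg QD total, Placebo only and" an overall column.

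On timing, Protocol 1.3 says "The study consists of an 8-week blinded treatment phase, followed by 8-week of blinded active arms extension phase", and "The total duration of the study participation, including extension and follow-up, will be approximately 18 weeks". SAP 16.1 collects AEs from first dose to the follow-up contact. SAP Appendix 2 assigns an event to the treatment phase only if it starts before the Week 8 visit. SAP 13 summarises exposure by phase and overall, but nothing in SAP 16 uses it as a denominator. SAP 16 plans no statistical comparison of safety data unless a section says otherwise.

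**The concern.** A crude percentage of patients with an event depends on how long they are watched. Here the columns differ in that respect by design. Within a dose-total column, patients randomised to the dose are followed from Week 0 and switchers only from Week 8. The placebo column ends at Week 8, even for placebo completers who decline the extension and are seen two weeks later. The same two weeks do count for a patient on a dose who declines.

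The maximum QTcF table has the same problem in another form. By the Time and Event Table, a patient who stays on a dose has five scheduled post-baseline ECG visits (Weeks 4, 8, 9, 16 and 18). A patient in the placebo column has at most two (Weeks 4 and 8), and a maximum over more readings tends to be higher.

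Safety and tolerability is the first secondary objective, and SAP 3.1 says the data will help select one or two doses. The whole-study tables are the only AE summaries described in SAP 16.1 to 16.2 that use the extension data. Side-by-side percentages will be read as a comparison whether or not a test is attached.

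**Working it through.** **Inputs from the documents.** Phases of 8 and 8 weeks plus 2 weeks of follow-up: 8 + 8 + 2 = 18 weeks, which reproduces the protocol's figure. 152 randomised 1:1:1:1 gives 152/4 = 38 per arm. Placebo patients switch 1:1:1, so 38/3 = 12.67 join each dose column.

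**Assumptions.** The documents give no AE rate. I take an 8-week placebo percentage p of 5%, 20% or 40%, the same hazard on drug and placebo, and no early withdrawal.

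**Observation windows.** Dose-arm patient who extends: 18 weeks. Dose-arm patient who declines: 8 + 2 = 10. Switcher, counted after Week 8: 18 − 8 = 10. Placebo column: 8.

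With full extension uptake, a dose-total column has 38 + 12.67 = 50.67 patients and 38×18 + 12.67×10 = 810.7 patient-weeks, a mean of 16.0 weeks against 8. Switchers sit in two columns, so the denominators can sum to 3×50.67 + 38 = 190 for 152 patients.

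**Constant hazard.** h = −ln(1 − p)/8 and F(w) = 1 − exp(−hw). With extension uptake u:

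dose total = [38(u·F(18) + (1 − u)·F(10)) + 12.67u·F(10)] / (38 + 12.67u)

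For p = 40% and u = 1: h = 0.06385, F(18) = 0.683, F(10) = 0.472, so (38×0.683 + 12.67×0.472)/50.67 = 63.0%.

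| Placebo, 8 weeks | Dose total, u = 1 | Dose total, u = 0.6 | Dosing time only (16 and 8 weeks), u = 1 |
|---|---|---|---|
| 5% | 9.7% | 8.6% | 8.6% |
| 20% | 35.7% | 31.9% | 32.0% |
| 40% | 63.0% | 57.8% | 58.0% |

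The last column shows that the artefact does not depend on the 2-week follow-up.

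**Front-loaded events.** Let the hazard after Week 8 be f·h in every arm, with u = 1. A dose-arm patient has an event with probability 1 − exp(−8h − 10fh), a switcher with probability 1 − exp(−10fh).

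| f | Dose total when placebo is 20% | Dose total when placebo is 40% |
|---|---|---|
| 0.5 | 26.1% | 49.1% |
| 0.25 | 20.7% | 40.3% |
| 0 | 15.0% | 30.0% |

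The reversal at f = 0 requires that switchers carry only the late hazard. If starting the drug restarts the early hazard, every patient in the column has probability p at f = 0, and the columns are equal.

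**Check of the remedy.** With a constant hazard, first events per 100 patient-years at risk are h×52.18×100 in every column: 146 for p = 20%, 333 for p = 40%. With a falling hazard they are not equal. For p = 40% and f = 0.5:

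- expected first events: 38×0.564 + 12.67×0.273 = 24.9
- weeks at risk: 38×11.40 + 12.67×8.56 = 541.6
- rate: 24.9/541.6 = 0.0460 per week, against 0.0639 on placebo, a ratio of 0.72

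For p from 5% to 40% the ratio is 0.69 to 0.72 at f = 0.5 and 0.53 to 0.57 at f = 0.25. If switchers restart the early hazard, it is 0.76 to 0.80 and 0.63 to 0.69.

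**The case against.** The strongest reply is that the valid comparison is already planned. Overall, SOC/PT, relationship, severity, serious infection, discontinuation, SAE, fatal-TEAE and QTcF tables are each specified for the treatment phase first, with every dose beside concurrent placebo. No formal safety tests are planned, the columns are named and defined, and exposure is tabulated elsewhere. All of that stands. A reader might infer that the SAP has no sound drug–placebo AE comparison, and the documents do not support that.

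A reader might also infer that a harmless drug is bound to look worse than placebo. That holds only if events keep arising after Week 8. With a late hazard at a quarter of the early one, the excess all but vanishes, and with no late events it can reverse. Uneven windows still make the percentages uninterpretable against placebo, and a column that could hide harm is no better than one that invents it.

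Two further readings go too far. Eighteen weeks is observation, not dosing, which lasts at most 16 weeks. Placebo observation does not end entirely at Week 8 either, since decliners attend a follow-up visit; the placebo column merely leaves it out.

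Finally, SAP 8 says that separate templates fix table content. They are not among the documents, so a footnote may exist there. What can be said is that the SAP text contains none.

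**Conclusion.** The point holds as a defect of display. The whole-study tables show crude percentages over a mean of about 16 weeks per dose column (full uptake) against 8 weeks of placebo, with no person-time denominator. Under a constant hazard and no drug effect, the false excess is about 5, 16 and 23 percentage points at placebo rates of 5%, 20% and 40%. At 60% uptake it is about 4, 12 and 18 points. These sizes rest on assumed AE rates and on events continuing to arise. Neither their size nor their direction is assured if events are front-loaded. The treatment-phase tables are unaffected. This is worth correcting as a cheap improvement and does not threaten the trial's conclusions.

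**What to change.** State in the SAP, and footnote on every whole-study table with these columns (16.1.1 to 16.2, and maximum QTcF in 16.4.1), that observation time differs between columns, that they are not comparable with placebo, and that the drug–placebo comparison is the 8-week treatment-phase table.

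Show patient-years at risk for each column. For any TEAE, SAE, serious infection, discontinuation and death, add patients with an event per 100 patient-years. Time at risk should run from the first dose of the column's treatment to the first event or the end of observation on that treatment.

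The footnote must cover the rates as well. They assume a roughly constant hazard and can understate risk on the drug if events come early, as the ratios of 0.69 to 0.72 show.

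Separately, reconcile the 4 mg QD total column. SAP 16.1.1 adds the placebo patients who switch to 4 mg QD, while the treatment-group table in SAP Appendix 1 adds those who switch to 4 mg BD.

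The cost is SAP wording, footnotes and a few derived variables from dates already collected. Each summary needs its own time to first event, which is why the rates are limited to the key summaries. Partial onset dates that Appendix 2 imputes to the first dose date would give almost no time at risk, so the SAP should say how those are handled.

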#### **16.1.1.1 Relationship to IP**

Relationship, as indicated by the Investigator, is classified into 5 grades: related, probably related, possibly related, unlikely to be related, and unrelated. A “related” TEAE is defined as a TEAE with a relationship to study medication as “related”, “probably related”, “possibly related” or “unlikely to be related” to study medication. If a patient reports the same AE more than once within that SOC/ PT, the AE with the worst case relationship to study medication will be used in the corresponding relationship summaries. All TEAEs in treatment phase will be summarized by SOC, PT and by relationship for each SHR-0302 dose level , placebo and overall. All TEAEs will also be summarized similarly for 8 mg QD total, 4 mg BD total, 4 mg QD total, Placebo only and overall during the whole study period.

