7.3.12 Definition of AE

Any untoward medical occurrence in a patient or clinical investigation subject, temporally associated with the use of a medicinal product, whether or not considered related to the medicinal product.

Note: An AE can therefore be any unfavorable and unintended sign (including an abnormal laboratory finding), symptom, or disease (new or exacerbated) temporally associated with the use of a medicinal product. For marketed medicinal products, this also includes failure to produce expected benefits (i.e., lack of efficacy), abuse or misuse.

Events meeting the definition of an AE include:

- Exacerbation of a chronic or intermittent pre-existing condition including either an increase in frequency and/or intensity of the condition
- New conditions detected or diagnosed after study treatment administration even though it may have been present prior to the start of the study
- Signs, symptoms, or the clinical sequelae of a suspected interaction
- Signs, symptoms, or the clinical sequelae of a suspected overdose of either study treatment or a concomitant medication (overdose per se will not be reported as an AE/SAE).

“Lack of efficacy” or “failure of expected pharmacological action” per se will not be reported as an AE or SAE. However, the signs and symptoms and/or clinical sequelae resulting from lack of efficacy will be reported if they fulfil the definition of an AE or SAE.

Events that **do not** meet the definition of an AE include:

- Medical or surgical procedure (e.g., endoscopy, appendectomy); the condition that leads to the procedure is an AE
- Situations where an untoward medical occurrence did not occur (social and/or convenience admission to a hospital)
- Anticipated day-to-day fluctuations of pre-existing disease(s) or condition(s) present or detected at the start of the study that do not worsen
- The disease/disorder being studied, or expected progression, signs, or symptoms of the disease/disorder being studied, unless more severe than expected for the subject's condition

AEs which meet all of the following criteria:

- Serious
- Unexpected (as per assessment according to safety information in Investigator Brochure)
- There is at least a reasonable possibility that there is a causal relationship between the event and the medicinal product

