will be classified as Suspected Unexpected Serious Adverse Reactions (**SUSARs**) and should be reported to the relevant ethics committee and to the relevant Health Authorities in accordance with applicable regulatory requirements for expedited reporting. Sponsor/designated CRO will report SUSARs to the ethics committee and relevant health authorities.

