9.3.4.4 Safety Analysis

Summaries of safety data will be based on the safety analysis set.

Adverse events will be grouped by Medical Dictionary for Regulatory Activities (MedDRA) system organ class (SOC) and preferred term (PT) and summarized by actual treatment.

Treatment emergent AEs are defined as AEs which commence on or after the time of start of IP administration. Adverse events without an onset date or time or AEs with an onset date of the date of IP administration but without an onset time will be defined as treatment emergent, except if an incomplete date (e.g., month and year) clearly indicates that the event started before administration of IP or if the AE stop date indicates that the event stopped before administration of IP.

Treatment emergent AEs will be summarized for each SHR0302 dose level and placebo. The number and percentage of subjects experiencing AEs and the number of TEAEs will be tabulated.

The following summaries will be presented:

- ✓ Overall summary of TEAEs.
- ✓ All TEAEs by SOC and PT.
- ✓ All TEAEs by SOC, PT, and severity.
- ✓ All TEAEs by SOC, PT, and relationship to IP.
- ✓ Serious AEs by SOC and PT.

Separate listings will be prepared for deaths and AEs leading to study discontinuation.

Observed values and actual changes from baseline of continuous laboratory parameters (hematology and biochemistry), dipstick urinalysis results evaluation (Normal, Abnormal Not Clinically Significant, or Abnormal Clinically Significant), vital signs, and ECG parameters will be summarized at each protocol scheduled time point, by actual treatment at each time point. Actual values and actual changes from baseline will be presented. Categorical outcomes will be summarized by frequency tabulations. Abnormal laboratory values will be flagged and will be identified in the listings. Microscopy data, if available, will be listed.

Shift tables representing categorical change of laboratory results from baseline to each post baseline visit will be presented. QTcF prolongation and ECG interpretations will be summarized by frequency tabulations.

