### **16.1.4 Serious Adverse Events (SAEs)**

A serious adverse event is any untoward medical occurrence that, at any dose:

- a. Results in death
- b. Is life-threatening
- c. Requires hospitalization or prolongation of existing hospitalization
- d. Results in disability/incapacity, or
- e. Is a congenital anomaly/birth defect

Document: \\ieedc-vnasc01\Biosdata\Reistone\SHR0302\CZA55021\Biostatistics

Author: [REDACTED]

Version Number:

Final v1.2

Version Date:

23Mar2021

Template No: CS\_TP\_BS016 Revision 5

Effective Date: 01Apr2018

Reference: CS\_WI\_BS005

- f. Medical or scientific judgement should be exercised in deciding whether reporting is appropriate in other situations, such as important medical events that may not be immediately life-threatening or result in death or hospitalization but may jeopardize the patient or may require medical or surgical intervention to prevent one of the other outcomes listed in the above definition. These should also be considered serious. Examples of such events are invasive or malignant cancers, intensive treatment in an emergency room or at home for allergic bronchospasm, blood dyscrasias or convulsions that do not result in hospitalization, or development of drug dependency or drug abuse.
- g. All events of possible drug-induced liver injury with hyperbilirubinaemia defined as ALT  $\geq$  3xULN and bilirubin  $\geq$  2xULN ( $>35\%$  direct) (or ALT  $\geq$  3xULN and INR  $>1.5$ , if INR measured) termed 'Hy's Law' events (INR measurement is not required and the threshold value stated will not apply to patients receiving anticoagulants).

On the Adverse Events page of the eCRF, serious adverse events are those events respond as "Yes" for item "Serious Criteria".

Summaries of all serious TEAEs and serious TEAEs Related to study medication in treatment phase by SOC and PT for each SHR0302 dose level, placebo and overall will be prepared. All serious TEAEs and serious TEAEs related to study medication will also be summarized similarly for 8 mg QD total, 4 mg BD total, 4 mg QD total, Placebo only and overall during the whole study period. Patients with missing relationship will be treated as probably related.

Listings will include all SAEs (serious TEAEs and serious Non-TEAEs). Listings for SAEs will include the start date, end date, severity, severity, relationship to study drug, action taken, outcome, SAE criteria, and a liver event or not, etc.

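### The SAP counts events graded as unlikely to be related among the related ones, without giving a reason, so any related-only table, certainly that of related serious TEAEs, is broader than the investigators' attribution

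*SAP*

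**What the plan says.** SAP 16.1.1.1 says that relationship, as indicated by the investigator, "is classified into 5 grades: related, probably related, possibly related, unlikely to be related, and unrelated". It then defines a related TEAE as one in any of the first four grades; the definition closes with "possibly related” or “unlikely to be related” to study medication". Where a patient has the same event more than once within a SOC/PT, the worst-case relationship is used. The section's own table is described as follows: "All TEAEs in treatment phase will be summarized by SOC, PT and by relationship for each SHR-0302 dose level , placebo and overall".

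SAP 16.1.4 plans "Summaries of all serious TEAEs and serious TEAEs Related to study medication in treatment phase by SOC and PT", and the same again for the whole study period. It adds: "Patients with missing relationship will be treated as probably related".

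Protocol 9.3.4.4 asks for "All TEAEs by SOC, PT, and relationship to IP" and for serious AEs by SOC and PT. It gives no cut-point for what counts as related. The only causality threshold in the protocol stands in section 7.3.12: "There is at least a reasonable possibility that there is a causal relationship between the event and the medicinal product". That is one of three conditions, with seriousness and unexpectedness, under which an event "will be classified as Suspected Unexpected Serious Adverse Reactions".

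**The concern.** A related-events table adds one thing to the all-events table: the investigator's view of cause. If only *unrelated* is left out, much of that is lost. A serious event that the investigator considered unlikely to be due to SHR0302 or placebo is printed in a table whose title says it was related.

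The SAP introduction to the design says that efficacy, safety and tolerability data from this study are to support the choice of one or two doses for further development. Safety is to be judged from descriptive counts, since SAP section 16 plans no between-group comparisons unless otherwise specified. A reader who takes the related counts as attributed toxicity would then read too much into them. If the added events are background events spread over all arms, the ratio of drug to placebo would also look smaller than the investigators' attribution implies.

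**Working it through.** The plan gives no figure on this point, so there is nothing to reproduce. The check is a comparison of texts, followed by an illustration.

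**Which outputs depend on the flag**

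- *Serious TEAEs related to study medication (SAP 16.1.4).* The table is restricted to related events, so the definition in 16.1.1.1 decides which events enter it. A serious event graded *unlikely* is counted.
- *All TEAEs by relationship (SAP 16.1.1.1).* This covers every TEAE. The text does not say whether the columns are the five grades or a related/not related split. With five grades, no cell is inflated; with two, the related column is. SAP section 8 leaves layout to output templates that are not part of the documents reviewed.
- *All other safety tables* (all TEAEs, serious infections, discontinuations, all serious TEAEs, deaths) do not use the flag.

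**Set against the protocol**

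The reasonable-possibility wording in Protocol 7.3.12 serves SUSAR classification and expedited reporting. Protocol 9.3.4.4, which governs the tables, has no cut-point. The SAP grouping is therefore looser than the one causality standard that the protocol states, but that standard was not written for tabulation.

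**Illustration**

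The documents give no AE rates; all rates here are assumed.

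- Patients per arm: 152 / 4 = 38 (Protocol 1.3 and 9.2.1).
- r = share of patients with at least one event graded *possibly related* or higher.
- u = further share whose highest grade is *unlikely*, taken as equal in both arms.
- Reported share = r + u. Reported count = 38 × (r + u).
- Risk ratio = (r_active + u) / (r_placebo + u).
- Risk difference = (r_active + u) − (r_placebo + u) = r_active − r_placebo.

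With r = 20% on active and 10% on placebo:

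| u | Active, patients | Placebo, patients | Risk ratio | Risk difference |
|---|---|---|---|---|
| 0% (unlikely not counted) | 7.6 | 3.8 | 20/10 = 2.00 | 10 points |
| 5% | 9.5 | 5.7 | 25/15 = 1.67 | 10 points |
| 10% | 11.4 | 7.6 | 30/20 = 1.50 | 10 points |
| 20% | 15.2 | 11.4 | 40/30 = 1.33 | 10 points |

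Each arm gains 38 × 5% = 1.9 to 38 × 20% = 7.6 patients, about 2 to 8. If u is zero in an arm, that arm does not change.

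Rates nearer to those of a serious-event table, again assumed: r = 5% on active and 0% on placebo gives 1.9 against 0 patients. With u = 5% the table shows 3.8 against 1.9, a ratio of 10/5 = 2.0, where the investigators' attribution had no related case on placebo. The difference stays at 5 points.

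**The case against.** The strongest reply is that this is a convention, stated in advance and applied alike to all arms, and that it errs on the inclusive side. It cannot remove from the table an event that an investigator thought related. The safety tables listed above are produced by arm whatever the causality grade. All AEs are listed, and the SAE listings carry the relationship to study drug, so a reader can regroup serious events by hand. All of this stands, and it limits the weight of the point.

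It does not justify the grouping. Caution is already built in: a missing relationship on a serious event counts as probably related, repeat events take the worst-case grade, and all serious TEAEs are tabulated anyway. Adding *unlikely* to the related group protects nothing further and blurs what the restricted table is for.

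Three stronger readings are tempting, and the documents do not support them:

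- *That the SAP contradicts the protocol's causality standard.* That standard governs SUSARs, and the protocol sets none for AE tables. Neither document defines the five grades or maps them to the SUSAR wording. It is a natural inference, not a stated rule, that an event graded *unlikely* falls short of a reasonable possibility.
- *That related counts are inflated in every arm and every table.* This depends on whether an arm has patients whose highest grade is *unlikely*, and the by-relationship table may show all five grades.
- *That the table loses power to show a dose signal.* No between-arm safety test is planned that could lose power. Equal additions change the ratio, not the difference. In the whole-study tables the additions need not be equal, because the active totals run over a longer period than the placebo-only group. That unequal follow-up affects every whole-study event table and does not come from this flag.

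**Conclusion.** The point holds in a limited form. SAP 16.1.1.1 places *unlikely to be related* among the related grades and gives no reason. The related serious TEAE tables in SAP 16.1.4 certainly inherit this; the table of all TEAEs by relationship does so only if its grades are collapsed. Where the flag applies, the count rises in any arm with patients whose highest grade is *unlikely*.

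The size cannot be found from the documents. The dilution shown above rests on assumed event rates and on equal additions in both arms. The sample size, the type I error rate and the efficacy conclusions are untouched. It is worth correcting because the correction is cheap and makes the related counts match what the investigators said.

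**What to change.** In SAP 16.1.1.1, define a related TEAE as one graded *related*, *probably related* or *possibly related*, and group *unlikely to be related* with *unrelated*. Keep the SAP 16.1.4 rule that treats a missing relationship as probably related. State that the by-relationship table and the listings show all five grades, so that either grouping can be derived.

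The cost is one sentence and one derivation flag, on data already collected. The small downside is a less inclusive related count. It is offset by the rule for missing relationship, by the table of all serious TEAEs, and by the display of all five grades.
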